3.1. Study Design

Adult male and female subjects who provide written, informed consent will enter a Screening period (28 days) during which they will be evaluated for eligibility, based on the Inclusion/Exclusion criteria.

At Day 1, eligible subjects will be randomized to study drug (see Section 3.2). Subjects will return to the study site for scheduled study visits at Weeks 2, 4, 8, 12, 18, 24, 26, 28, 32, 36, 42 and 48. After completion of the Week 24 assessments and procedures, subjects on placebo will be re-randomized 1:1:1 to filgotinib, or GS-9876, or GS-4059, in a blinded fashion. Dosing will continue through Week 48.

Subjects who discontinue study drug for any reason (other than noncompliance) may continue to participate in scheduled study visits and procedures, as long as deemed medically appropriate by the investigator. Subjects who discontinue all study participation will have an early termination (ET) visit; these subjects, and those who complete the study, should return to the study site for a follow-up visit, 4 weeks after the last dose of study drug (subjects who have discontinued study drug \geq 4 weeks prior to the ET/Week 48 visit, do not need a follow up visit).

Figure 3-1. Study Design Schematic

For details regarding dosing and blinding, see Section 5.7.

For details regarding concomitant and excluded medications, see Section 5.8.

For study visit schedule and procedures, including clinical laboratory tests and **CCI**, see Schedule of Activities in Section 6 and Appendix 2.

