6.2.2. Day 1 Assessments

At Day 1, after the subject's eligibility for the study has been confirmed, the subject will be randomized into the study to receive one of four study dosing regimens.

Subjects should be instructed to fast (no food or drink, except water), starting from midnight (00:00) or earlier, as appropriate, on the evening prior to D1 visit to ensure an approximate 8-hour fast prior to the blood sample collection under fasting condition the next morning.

VAS and subject reported QOLs assessments are recommended to be completed before any other study procedures. Invasive study procedures such as blood draws should be done at the end of a study visit. The following will be performed and documented at Day 1 prior to dosing:

- Randomization
- Vital Signs, including weight

- Symptom-directed PE
- ESSDAI (lab results and PFTs as applicable from screening will be used)
- PE for domains of ESSDAI
- 28 Swollen and Tender Joint count
- Physician's Global Assessment of SjS disease activity
- Physician's Global Assessment of concomitant RA or SLE disease activity as applicable
- Obtain urine sample for:
 - Urinalysis with spot protein/microalbumin/creatinine
 - Urine Pregnancy Test (female subjects of child bearing potential only)
 - Fasting urine for biomarker
- Obtain blood samples for:
 - Hematology, ESR as applicable, chemistry and hsCRP
 - Complement (C3, C4, CH50), and CK
 - Fasting lipid profile, as outlined in [Appendix 6](#)
 - Biomarker samples
 - Autoantibodies: deamidated gliadin peptide antibodies (anti DGP IgA or IgG); Anti endomysial antibodies (EMA), RF, CCP (cyclic citrullinated peptide), dsDNA, ANA, IgA anti tTA (tissue transglutaminase antibodies)
 - CCI 
- VAS
- Subject reported QOLs
- Other questionnaires addressing disease, activity and fatigue may be provided when and where available.
- Treatment Satisfaction Questionnaire for Medication (TSQM)

- CCI [REDACTED]
- 12-Lead ECG
- CCI [REDACTED]
- CCI [REDACTED]
- CCI [REDACTED]
- CCI [REDACTED]
- CCI [REDACTED]
- CCI [REDACTED]
- Drug dispensing
- Adverse Events
- Concomitant medications

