Subjects should be instructed to fast (no food or drink, except water), starting from midnight (00:00) or earlier, as appropriate, on the evening prior to Week 12 visit to ensure an approximate 8-hour fast prior to the blood sample collection under fasting condition the next morning.

The following assessments will be completed at each visit or as specified in the Schedule of Assessments in [Appendix 2](#).

Note: VAS and Subject reported QOL assessments are recommended to be completed before any other study procedures. Invasive study procedures such as blood draws should be done at the end of a study visit.

- Vital Signs, including weight
- Symptom-directed PE
- ESSDAI
- PE for domains of ESSDAI
- 28 Swollen and Tender Joint count
- Physician's Global Assessment of SjS disease activity
- Physician's Global Assessment of concomitant RA or SLE disease activity as applicable
- Obtain urine sample for:
 - Urinalysis with spot protein/ microalbumin/creatinine
 - Urine Pregnancy Test (female subjects of child bearing potential only)
 - Fasting urine for biomarker
- Obtain blood samples for:
 - Hematology, ESR as applicable, chemistry and hsCRP
 - Viral Monitoring for HCV as applicable (see Exclusion criteria, Section 4.3)
 - Autoantibodies: deamidated gliadin peptide antibodies (anti DGP IgA or IgG); Anti endomysial antibodies (EMA), RF, CCP, dsDNA, ANA, SSA, SSB, IgA anti tTA (tissue transglutaminase antibodies)
 - Complement (C3, C4, CH50), and CK
 - Cryoglobulins, total Ig, quant IgG, IgA, and IgM, serum and urine immunofixation
 - Fasting lipid profile
 - PK samples, collected prior to study drug administration (pre-dose)
 - Biomarker samples

- VAS
- Subject reported QOLs
- TSQM
- CCI [REDACTED]
- 12-Lead ECG
- PFTs (at selected sites)
- CCI [REDACTED]
- CCI [REDACTED]
- CCI [REDACTED]
- CCI [REDACTED]
- CCI [REDACTED]
- CCI [REDACTED]
- Drug dispensing
- Drug accountability
- Adverse Events
- Concomitant medications

6.8. Week 18

Subject should be instructed **to hold their dose of study drugs** in the morning of the visit. The dose should be taken at the clinic as soon as possible after the pre-dose biomarker blood draw is completed, so PK samples and post-dose biomarker samples can be drawn approximately 2 hours after dose.

The following assessments will be completed at each visit or as specified in the Schedule of Assessments in [Appendix 2](#).

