6.16. Study Assessments

This study consists of 14 scheduled visits plus a follow up visit 4 weeks after study drug is stopped, with total study duration of 48 weeks (+4 weeks).

The study procedures to be conducted for each subject enrolled in the study are described in the following sections. In addition, [Appendix 2](#) presents the study procedures in tabular form.

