7.2.1. Summaries of Numeric Laboratory Results

Descriptive statistics will be provided by treatment group for each laboratory test specified in the study protocol as follows:

- Baseline values
- Values at each postbaseline visit
- Change and percentage change from baseline at each postbaseline visit.

Descriptive statistics will be provided by treatment group for the following laboratory tests:

- Hematology
 - Hematocrit
 - Hemoglobin
 - Platelet count
 - Red blood cell count

- White blood cell (WBC) count
- Mean corpuscular volume
- Lymphocytes
- Monocytes
- Neutrophils
- Eosinophils
- Basophils
- Chemistry
 - Alanine aminotransferase (ALT)
 - Aspartate aminotransferase (AST)
 - Alkaline phosphatase (ALP)
 - Total bilirubin
 - Serum creatinine
 - Creatinine clearance by Cockcroft-Gault formula
 - Creatinine phosphokinase (CPK)
 - Glucose
 - Triglycerides
 - Total cholesterol
 - High Density Lipoprotein (HDL)
 - LDL (Low Density Lipoprotein)
 - LDL/HDL ratio

Change from baseline to a postbaseline visit will be defined as the visit value minus the baseline value. The mean, median, Q1, Q3, minimum, and maximum values will be displayed to the reported number of digits; SD values will be displayed to the reported number of digits plus 1.

Median (Q1, Q3) of the observed values for the laboratory tests specified above will be plotted using a line plot by treatment group and visit.

In the case of multiple values within the visit, data will be selected for analysis as described in Section 3.8.3

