7.2.2.1. Treatment-Emergent Laboratory Abnormalities

Treatment-emergent laboratory abnormalities for the entire study period and in subjects discontinued treatment prematurely are defined as values that increase at least 1 toxicity grade from baseline at any postbaseline time point, up to and including the date of last dose of study drug plus 30 days for subjects who permanently discontinued study drug, or the last available date in the database snapshot for subjects who were still on treatment at the time of an interim analysis. If the relevant baseline laboratory value is missing, any abnormality of at least Grade 1 observed within the time frame specified above will be considered treatment emergent.

For the analyses of active treatment period, the baseline is the day of the first dose of active study drug administration.

For the analyses of placebo-controlled period, the laboratory abnormality occurring after Week 24 visit and no later than 30 days after the last dose of study drug is included only if subject does not continue treatment after Week 24.

The listing of all laboratory abnormalities will be provided.

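### Glucose has a fasting baseline but only 3 of 12 on-treatment visits are fasting, and the SAP compares every visit with that baseline, so meals can appear as glucose rises in every arm

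*SAP*

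**What the plan says.** **Fasting.** Protocol 6.2.2 has subjects fast "on the evening prior to D1 visit to ensure an approximate 8-hour fast prior to the blood sample collection under fasting condition". Protocol 6.7 (Week 12) gives the same instruction, "starting from midnight (00:00) or earlier, as appropriate, on the evening prior to Week 12 visit to ensure an approximate 8-hour fast", and Protocol 6.9 (Week 24) and 6.14 (Week 48/ET) repeat it. The fasting row in both schedules (Protocol Appendix 2, SAP Appendix 1) marks those four visits and no others. Protocol 5.7 allows study drug to be taken with or without food.

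**Sampling.** Protocol Appendix 6 lists glucose under chemistry. Protocol Appendix 2 has chemistry drawn at every visit from Screening to Follow-up. The lipid profile is drawn only at the four fasting visits.

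**Analysis.**
- SAP 7.2 takes as baseline the last value at or before first dose, normally the Day 1 sample. For the active period of subjects who switch from placebo it is the last value up to the day of first active dose, normally the Week 24 sample.
- SAP 7.2.1 names glucose and reports "Change and percentage change from baseline at each postbaseline visit", with a by-visit line plot of observed values.
- SAP 7.2.2.1 defines treatment-emergent abnormalities as "values that increase at least 1 toxicity grade from baseline at any postbaseline time point".
- SAP 7.2.2.3 classifies each subject by the worst post-baseline grade.
- SAP 7.2.4 gives grade shift tables for Weeks 12 and 24.

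No SAP section limits, splits or flags glucose by fasting status.

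**The concern.** A change from baseline is interpretable when both values are taken under the same conditions. Here the baseline is normally fasting, while most later glucose samples are taken with no instruction about food. A subject who has eaten before one of those visits can show a rise that has nothing to do with drug.

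The graded tables are more exposed than the by-visit summaries. A single sample after food, at any visit, can set a subject's worst grade.

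Safety and tolerability is a secondary objective, and these descriptive tables are the main laboratory output for it. Up to Week 24 the placebo arm shows how large the background is. After Week 24 all continuing placebo subjects move to active drug, so the later tables have no such reference.

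**Working it through.** **1. Visit count.** Protocol 3.1 gives "scheduled study visits at Weeks 2, 4, 8, 12, 18, 24, 26, 28, 32, 36, 42 and 48", which is 12 on-treatment visits. Adding Screening and Day 1 gives 12 + 2 = 14. This agrees with Protocol 6.16, which states "14 scheduled visits plus a follow up visit".

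**2. Visits that match the fasting baseline.**

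| Period | On-treatment visits | Fasting | No fasting instruction |
|---|---|---|---|
| Weeks 2–24 | 6 | 2 (Weeks 12, 24) | 4 (Weeks 2, 4, 8, 18) |
| Weeks 26–48 | 6 | 1 (Week 48) | 5 (Weeks 26, 28, 32, 36, 42) |
| Total | 12 | 3 (25%) | 9 |

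With the follow-up visit, which also draws chemistry without a fasting instruction, it is 3 of 13.

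**3. Which outputs are exposed.**
- Change and percentage change (SAP 7.2.1): the rows for the 9 visits compare a sample of unknown fasting status with a fasting one. The rows for Weeks 12, 24 and 48 are normally like for like.
- Treatment-emergent and marked grades (SAP 7.2.2): all visits feed one worst grade per subject, so the conditions cannot be separated afterwards.
- By-visit plot: it shows observed values, so fasting and unrestricted visits alternate along one line.
- Grade shift tables (SAP 7.2.4): both visits are fasting, so these are not affected.
- Lipids: drawn only at fasting visits, so not affected.

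**4. How worst-grade counting accumulates.** The documents give no per-visit rates, so these are assumptions. Let qF be the chance of a grade rise at a fasting visit and qN at a visit without the instruction, with visits independent and no drug effect:

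P(at least one) = 1 − (1 − qF)^(fasting visits) × (1 − qN)^(other visits)

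Take qF = 1%. By Week 24 there are 2 fasting and 4 other visits; by Week 48, 3 and 9. For example, qN = 5% by Week 24 gives 1 − 0.99² × 0.95⁴ = 1 − 0.9801 × 0.8145 = 20.2%.

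| qN | By Week 24 | By Week 48 |
|---|---|---|
| 1% (as if all visits were fasting) | 5.9% | 11.4% |
| 2% | 9.6% | 19.1% |
| 5% | 20.2% | 38.8% |
| 10% | 35.7% | 62.4% |

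On the fasting visits alone the figures are 1 − 0.99² = 2.0% and 1 − 0.99³ = 3.0%.

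**5. How far the size depends on unknowns.** A simulation to Week 24 assumed a fasting mean of 92 mg/dL, between-subject SD 7 and within-subject SD 5. Samples after food were 12 mg/dL higher with within-subject SD 15. Among subjects at or below the threshold at baseline, the share with any value above it over all six visits was:
- 77% at a threshold of 110 mg/dL, 32% at 125, 5.6% at 140 and 0.1% at 160
- about 52% at 110 if only half of the unrestricted samples follow food
- about 11% at 110 if the meal effect is +2 mg/dL with SD 6

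At 110, the fasting visits alone give 2.4%. The direction is the same in every case; the size ranges from negligible to dominant.

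**The case against.** **Bias against placebo.** A reader might infer that the active-versus-placebo comparison is distorted. The documents do not support that. All four arms share one schedule, treatment is blinded, and placebo runs concurrently to Week 24, so the artefact falls on every arm alike. This objection stands in full for that period.

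**Meals as a certainty.** A reader might also infer that meals will appear as rises at the 9 visits. Those visits are uncontrolled, not known to follow food. Dosing is in the morning, and some subjects may arrive without having eaten. The supportable wording is that meals can appear as rises.

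**Grading threshold.** SAP 7.2.2 grades by CTCAE, but Protocol Appendix 4 gives only a link and one unrelated row. Which glucose value earns a grade, and whether the scale conditions on fasting, cannot be read from the documents. No figure that equates a value above a chosen limit with a grade increase is a property of this plan.

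**A hidden drug effect.** It is tempting to say that the background hides a true effect. In the simulation at 110 mg/dL, a drug effect of +6 mg/dL moves the fasting-visit rate from 2.4% to 11.8% (9.4 points) and the all-visit rate from 77% to 89% (12 points). The ratio shrinks but the difference does not, and at about 35 subjects per arm neither contrast is decisive.

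**Limited reach.** The laboratory tables are descriptive, glucose is neither an adverse event of special interest nor a laboratory discontinuation criterion, and the fasting visits can be identified from SAP Appendix 1. This limits the importance of the point. It does not help with the worst-grade tables, where a reader cannot recover which samples were fasting.

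**Restricting the grades to fasting visits.** This would leave the first scheduled graded value at Week 12 and give placebo switchers one scheduled value on active drug. It would drop early, severe and low values, and the unscheduled values that SAP 3.8.2 includes in the maximum grade. That objection stands, so the graded tables should keep all samples.

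**Conclusion.** The concern holds in a limited form. The plan compares glucose from 9 of 12 on-treatment visits, with no fasting instruction, with a baseline that is normally fasting, and it has no rule to separate the two. Within-arm changes and treatment-emergent grade increases can be raised by meals in every arm, placebo included. Up to Week 24 this adds background without by itself biasing the comparison with placebo. After Week 24, with 1 of 6 visits fasting and no concurrent placebo, nothing in the tables would reveal it.

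The visit counts, the baseline rule and the lack of a fasting rule come from the documents. The size does not: it depends on the meal effect, the share of samples taken after food and the grading threshold, none of which the documents give. The conclusion also assumes that fasting instructions are followed and that the Day 1 sample exists; if it is missing, the baseline falls back to Screening, which has no fasting instruction.

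**What to change.** - **SAP 7.2.1:** report glucose change and percentage change from baseline for fasting samples only: Weeks 12, 24 and 48/ET, against Day 1, or against Week 24 for the active period of placebo switchers. Include fasting ET samples whatever visit they are assigned to, because SAP 3.8.2 moves ET data to the next scheduled visit, which may not be a fasting one. Show samples without a fasting instruction in a separate, labelled row as observed values.
- **SAP 7.2.2:** keep the all-sample treatment-emergent and marked glucose grades, including unscheduled, Grade 3 or 4 and low values. Add a fasting-sample-only row for high glucose.
- **By-visit plot:** mark the fasting visits.

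The cost is SAP wording, one extra row per table and a fasting flag in the laboratory programs. Visits, samples and subject management do not change. The fasting-only row will have few time points, which is why the all-sample row stays beside it.

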7.2.2. Graded Laboratory Values

The Common Terminology Criteria for Adverse Events (CTCAE) will be used to assign toxicity grades (0 to 4) to laboratory results for analysis. Grade 0 includes all values that do not meet the criteria for an abnormality of at least Grade 1. For laboratory tests with criteria for both increased

and decreased levels, analyses for each direction (i.e., increased, decreased) will be presented separately.

7.2.2.1. Treatment-Emergent Laboratory Abnormalities

Treatment-emergent laboratory abnormalities for the entire study period and in subjects discontinued treatment prematurely are defined as values that increase at least 1 toxicity grade from baseline at any postbaseline time point, up to and including the date of last dose of study drug plus 30 days for subjects who permanently discontinued study drug, or the last available date in the database snapshot for subjects who were still on treatment at the time of an interim analysis. If the relevant baseline laboratory value is missing, any abnormality of at least Grade 1 observed within the time frame specified above will be considered treatment emergent.

For the analyses of active treatment period, the baseline is the day of the first dose of active study drug administration.

For the analyses of placebo-controlled period, the laboratory abnormality occurring after Week 24 visit and no later than 30 days after the last dose of study drug is included only if subject does not continue treatment after Week 24.

The listing of all laboratory abnormalities will be provided.

7.2.2.2. Treatment-Emergent Marked Laboratory Abnormalities

Treatment-emergent marked laboratory abnormalities are defined as values that increase from baseline by at least 3 toxicity grades at any postbaseline time point, up to and including the date of the last dose of study drug plus 30 days for subjects who permanently discontinued study drug or the last available date in the database snapshot for subjects who were still on treatment at the time of a primary Week 24 analysis. If the relevant baseline laboratory value is missing, any Grade 3 or 4 values observed within the timeframe specified above will be considered treatment-emergent marked abnormalities.

Same rules as in the Section [7.2.2.1](#) apply for determination of TE abnormality in the placebo-controlled period and entire study period.

7.2.2.3. Summaries of Laboratory Abnormalities

The following summaries (number and percentage of subjects) for treatment-emergent laboratory abnormalities will be provided by lab test and treatment group; subjects will be categorized according to the most severe postbaseline abnormality grade for a given lab test:

- Treatment-emergent laboratory abnormalities
- Treatment-emergent grade 3 or 4 laboratory abnormalities
- Treatment-emergent marked laboratory abnormalities

The summaries of treatment-emergent laboratory abnormalities will be presented by treatment group and highest grade for the placebo-controlled and entire study period. The listing of all laboratory abnormalities will be provided.

For all summaries of laboratory abnormalities, the denominator is the number of subjects with nonmissing postbaseline values, with the baseline determined per Section 7.2.

By-subject listings of treatment-emergent Grade 3 or 4 laboratory abnormalities and marked laboratory abnormalities will be provided by subject ID number and visit in chronological order. This listing will include all test results that were collected throughout the study for the lab test of interest, with all applicable severity grades displayed.

7.2.3. Liver-related Laboratory Evaluations

Liver-related abnormalities after initial study drug dosing will be examined and summarized using the number and percentage of subjects who were reported to have the following laboratory test values for postbaseline measurements:

- Aspartate aminotransferase (AST): (a) > 3 times of the upper limit of reference range (ULN); (b) > 5 x ULN; (c) > 10 x ULN; (d) > 20 x ULN
- Alanine aminotransferase (ALT): (a) > 3 x ULN; (b) > 5 x ULN; (c) > 10 x ULN; (d) > 20 x ULN
- AST or ALT: (a) > 3 x ULN; (b) > 5 x ULN; (c) > 10 x ULN; (d) > 20 x ULN
- Total bilirubin: > 2 x ULN
- Alkaline phosphatase (ALP) > 1.5 x ULN
- AST or ALT > 3 x ULN and total bilirubin: (a) > 1.5 x ULN; (b) > 2 x ULN

The summary will include data from all postbaseline visits on active treatment up to 30 days after the last dose of study drug. For individual laboratory tests, subjects will be counted once based on the most severe postbaseline values. For both the composite endpoint of AST or ALT and total bilirubin, subjects will be counted once when the criteria are met at the same postbaseline visit date. The denominator is the number of subjects in the Safety Analysis Set who have nonmissing postbaseline values of all relevant tests at the same postbaseline visit date.

The analyses will be presented for the placebo-controlled period and entire study period.

A listing of subjects who met at least 1 of the above criteria will be provided.

